Subjects Terminating Study	the Criteria on completion of the trial: 1. Progression of disease 2. Death 3. Inability to recover to \leq NCI CTC AE Grade 1 or baseline within 14 days after dose interruption 4. NCI CTC AE Grade 4 (nephrotic syndrome) in routine urinalysis or 24-hour urine protein quantification; CTC AE Grade 4 abnormal hepatic function and hemorrhage Criteria on premature discontinuation: 1. The subject becomes pregnant. 2. The investigator judges the termination of the study in the subject's best interest; 3. The subject or his/her legal representative requestes withdrawal from the study; 4. The subject is lost to follow-up 5. Serious violation from the study protocol
End of the whole trial	The whole trial ends 9 months after the end of enrollment for the expansion part.
Statistical analysis:	SAS 9.2 software is used for analysis, where the pharmacokinetic parameters are calculated using WinNonlin software. The detailed statistical method will be provided in the statistical analysis plan. In the randomized comparison part, statistical analysis and comprehensive evaluation will be performed for the primary parameters including safety and tolerability (overall incidence of adverse events, incidence of G3/4 adverse events, incidence of serious adverse events, incidence of adverse events leading to dose interruption and permanent discontinuation of the drug) and secondary parameters including the efficacy, as to determine the recommended dose for phase II/III trials. In the expansion part, the safety, tolerability and efficacy of Fruquintinib 5mg 3-week on/1-week off are further evaluated in patients with advanced colorectal cancer. The primary endpoints (safety, tolerability and progression-free survival at Week 16) are analyzed three months after the inclusion of the last subject in the expansion part. The overall survival is analyzed 9 months after the inclusion of the last subject in the expansion part.
Efficacy	To perform statistical description of objective response rate (proportion of subjects with complete response or partial response as the optimal overall response, according to RECIST1.1 criteria), DCR, DOR, PFS and OS.

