8.1 Primary and secondary research variables

Primary variables:

Overall incidence of adverse events

Incidence of Grade 3/4 adverse events

Incidence of serious adverse events

Incidence of adverse events leading to permanent discontinuation

Incidence of adverse events leading to interruption/reduced dose

16-week progression-free survival rate

Secondary variable:

Effectiveness:

"Event occurrence date" variable: Calculated since the day when the informed consent is signed. If no event is observed, there is no date of end, and a so called cutoff observation has to be considered for analysis. The cutoff date is: The last date, such as for "last tumor measurement", "last medication registration", or "last visit".

Secondary efficacy variables include objective response rate, disease control rate, duration of response, progression-free survival, and overall survival.

Objective response rate (ORR): defined as the incidence of confirmed complete response (CR) or partial response (PR), the target lesions and non-target lesions are evaluated with validated radiological method and judged in accordance with RECIST criteria 1.1.

Progression-free survival (PFS): defined as the time from the signature of informed consent form to the first recording of progression of disease (PD) or date of death, whichever comes first. If no PD is observed, the censoring date should be the date of the last tumor measurement.

Overall survival (OS): defined as the time from the signature of informed consent form to date of death for any reason. If no death is observed, the last follow-up date is regarded as the censoring date.

Disease control rate (DCR): defined as the incidence of confirmed complete response (CR), partial response (PR) and stable disease (SD), the target lesions and non-target lesions are

evaluated with validated radiological method and judged in accordance with RECIST criteria 1.1.

Duration of response: defined as the time from the first recording of CR or PR to the first finding of PD for patients who have achieved response. For those with no record of PD after CR or PR, the censoring date is the date of the last tumor measurement.

Safety and Tolerability:

Safety and tolerability of the treatment are evaluated by incidence and severity of adverse events, laboratory tests, vital signs, ECG, LVEF, and ECOG performance status.

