8.2.2 Statistical Methods

Efficacy Analysis:

Randomized comparison part-secondary efficacy endpoint analysis:

The inter-group difference of objective response rate is compared by CMH Chi-square test.

Secondary efficacy endpoint analysis: Descriptive statistical analysis.

Progression-free survival is analyzed by Kaplan-Meier method;

Overall survival is analyzed by Kaplan-Meier method;

The inter-group difference of disease control rate is compared by CMH Chi-square test;

The duration of response is analyzed by Kaplan-Meier method; the median time to response and its 95% confidence interval are listed for the two groups.

Expansion part- primary efficacy endpoint analysis:

The 16-week progression-free survival rate is calculated in patients with advanced colorectal cancer who have failed with standard care and are receiving drug administration of 5 mg qd 3-week on/1-week off in the study. Secondary endpoints are analyzed by descriptive statistical analysis.

At the end of the trial, the survival (including median survival and 9-month survival rate) in patients with advanced colorectal cancer who have failed with standard care and are receiving drug administration of 5 mg qd 3-week on/1-week off is analyzed.

Safety analysis:

Safety analysis population: The safety analysis population includes the patients signing the informed consent who receive at least one dose of the treatment.

All safety parameters are summarized, and are tabulated by the safety population.

The frequency table (overall and by intensity) of adverse events is listed by system organ class. In the table of the overall incidence of adverse event, subjects with the same adverse event more than once is only counted once in the frequency table.

Shift table and frequency table are used simultaneously for summary of laboratory data according to sampling timepoint.

All the AEs and abnormal laboratory variables are evaluated according to CTCAE v4.0 grading system.

ECOG performance status will be summarized by descriptive statistics. Vital signs, ECG, and echocardiography will be described by tabulation.

During the randomized comparison part, inter-group differences are compared by CMH Chi-square test, based on the primary safety endpoints.

The overall incidence of adverse events, incidence of G3/4 adverse events, and severe adverse events are compared between the two groups;

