4.6.2 Overall Response Period

The overall response period is the period from the time when it complies with the CR or PR criteria (whichever is first measured) to the time when disease relapse or progression of disease is first recorded actually (the minimum measurement recorded during the trial is used for reference of progression of disease). The overall duration of response is the period from the time when the measurement first meets the CR criteria to the time when disease or progression of disease is first recorded.

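### Duration of response censors a responder who dies without recorded progression, and section 8.2.2 labels the listed median as time to response

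*Protocol*

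**What the plan says.** Protocol section 8.1 gives DOR as "defined as the time from the first recording of CR or PR to the first finding of PD for patients who have achieved response". Its censoring rule is: "For those with no record of PD after CR or PR, the censoring date is the date of the last tumor measurement". Death appears in neither sentence. The PFS definition in the same section runs to the "first recording of progression of disease (PD) or date of death, whichever comes first".

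Section 8.2.2 sets the method, "The duration of response is analyzed by Kaplan-Meier method", and continues in the same sentence: "the median time to response and its 95% confidence interval are listed for the two groups". Time to response is not among the variables defined in section 8.1.

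Two other places bear on the point. The efficacy row of the synopsis's statistical section includes DOR among the endpoints to be described ("DCR, DOR, PFS and OS"). Appendix 2, section 4.6.2, lets the response period run "to the time when disease relapse or progression of disease is first recorded actually", also without naming death.

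**The concern.** There are two separate faults of wording.

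The first is the event definition. A responder can die between scans, or after stopping treatment, before any progression is recorded. That death ends PFS, but for DOR the patient is treated as if the response were still running when last seen. Kaplan-Meier then lets the remaining responders stand in for the dead one. A response that has ended in death cannot continue, so this censoring is not neutral.

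The second is the listed statistic. DOR starts at first CR or PR. Under the general rule in section 8.1, which counts event times from signature of consent, time to response would stop at first CR or PR. The two quantities meet at one date and share no interval. Taken literally, section 8.2.2 attaches to the DOR analysis a median that says nothing about durability.

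At stake is one secondary endpoint of the randomized part. The secondary objectives (synopsis and section 2.2) name it for comparison between the two regimens.

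**Working it through.** The plan states no DOR figure, target or power, so there is nothing to reproduce. The check covers the wording, the direction of the effect and its possible size.

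**1. A responder who dies without recorded PD, under each rule**

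| Place | Treatment of that death |
|---|---|
| Section 8.1, PFS | Event at date of death |
| Section 8.1, DOR | Censored at last tumour measurement |
| Appendix 2, section 4.6.2 | Not addressed; period ends at relapse or progression |

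**2. Direction.** Let n responders be at risk after one scan. Before or at the next scan, d die without recorded PD and p are found to have PD. The Kaplan-Meier factor for the interval is:

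- PD or death as event: (n - d - p)/n
- as written, with the d deaths moved back to the previous scan and censored: (n - d - p)/(n - d)

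The second is never smaller than the first. It is larger whenever d > 0 and some responders remain. This takes scans as falling on a common schedule counted from first response; off-schedule scans can shift a very small-sample curve locally. With d = 0 the two rules agree.

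**3. Size.** Let λ be the constant hazard of a response ending for any reason, and q the share of endings that are deaths without recorded PD. The PD-or-death median is ln2/λ. The rule as written estimates ln2/[(1-q)λ]. The ratio is 1/(1-q). The documents do not give q, so a range is assumed:

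| q (assumed) | Median ratio 1/(1-q) |
|---|---|
| 0% | 1.00 |
| 5% | 1.05 |
| 10% | 1.11 |
| 20% | 1.25 |
| 30% | 1.43 |

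The ratio arises even if PD risk and death risk are independent; it comes from not counting the deaths.

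**4. Check with the scan interval.** Scans are every 8 weeks (study flowchart, note 1). A simulation of 200,000 responders used that interval and an assumed true PD-or-death median of 24 weeks. The DOR probability at 24 weeks was about 0.50 with death as an event. Under the rule as written it was 0.53, 0.57 and 0.60 at q = 10%, 20% and 30%. The continuous-time values, 0.5^(1-q), are 0.54, 0.57 and 0.62, so the direction and rough size agree.

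**5. Chance that any responder is affected.** Section 3.1.2 reports 2 patients with PR+MR among 17 evaluable (4 mg daily) and 3 among 18 (5 mg 3/1). Section 8.1 counts only confirmed CR or PR, so these are upper bounds on responders at the interim. The chance of at least one such death among R responders is 1 - (1-q)^R:

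| q (assumed) | R = 2 | R = 3 |
|---|---|---|
| 5% | 10% | 14% |
| 20% | 36% | 49% |
| 30% | 51% | 66% |

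**6. Sensitivity with few responders.** Take three responders, in an example built to contain a death: PD at 8 weeks, death at 16, ongoing at 24. With death as an event, S falls to 2/3 and then 1/3, and the median is 16 weeks. With the death censored, S stays at 2/3 and the median is not reached. This shows how far one death can move the estimate, not what to expect.

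**The case against.** **Progression-only DOR agrees with the protocol's own criteria.** Appendix 2, section 4.6.2, also ends the response period at relapse or progression. DOR and PFS are separate endpoints, and a difference between them is not in itself a contradiction. This stands in part: DOR is too long only relative to a progression-or-death definition, which the protocol does not adopt. But Appendix 2 does not say what to do with a death. The instruction to censor is section 8.1's own.

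**The PFS text is loose too.** It also says that a patient with no PD is censored at the last tumour measurement. That suggests general drafting looseness. Even so, PFS names death as an event and DOR does not.

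**A reader might infer that DOR will certainly be overestimated.** The documents do not support that. At least one responder must die without recorded PD, and no rate is given. At q = 5% the chance is only 10% to 14% with 2 or 3 responders.

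**A reader might also infer that no DOR median will be produced.** That does not follow. Section 8.2.2 prescribes Kaplan-Meier for DOR and the synopsis lists DOR for description. In a sentence about DOR, an undefined time to response is most likely a mislabelled DOR median.

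**No decision rests on DOR.** Section 8.2.2 heads the secondary efficacy analysis as descriptive and gives no between-arm test for DOR. The expansion part does not list DOR as an endpoint. The regimen choice in section 3.1.2 cites DCR, PFS and safety. With so few responders, the median is very imprecise under either rule. All of this stands and keeps the point minor.

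**Conclusion.** The point holds as two faults of wording.

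Section 8.1 censors a death without recorded PD for DOR and counts the same death for PFS. If such a death occurs, Kaplan-Meier DOR is too long relative to a progression-or-death definition. The median is inflated 1.05 to 1.43 times for an assumed 5% to 30% share of such endings. Those factors rest on constant hazards and on a share the documents do not give; with no such death the inflation is nil.

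Section 8.2.2 names an undefined and different quantity as the statistic listed for DOR, most likely by mislabelling.

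The importance is low. DOR is secondary and descriptive, responders at the interim number at most 2 and 3, and the trial's main conclusions are not affected.

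**What to change.** - **Section 8.1:** define DOR as the time from first recorded CR or PR to PD or death from any cause, whichever comes first. Censor only patients alive without PD, at their last tumour measurement.
- **Section 8.2.2:** replace median time to response with median duration of response, keeping the 95% confidence interval. If time to response is also wanted, define it as a separate variable in section 8.1.

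The cost is two wording changes. No new data are needed, because death and tumour assessments are already collected for PFS and OS. The reported DOR may be slightly shorter.

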8.2 Statistical and analytical methods

8.2.1 Data Set Analyzed

Intent-to-treat analysis set (ITT set): According to the intent-to-treat analysis principle, ITT set includes all randomized patients, and is analyzed by the groups into which the patients are assigned for randomization, whether they receive the investigational treatment or not.

Safety Analysis Set (SAS set): The SAS set includes all randomized patients who receive at least 1 dose of the investigational drug.

8.2.2 Statistical Methods

Efficacy Analysis:

Randomized comparison part-secondary efficacy endpoint analysis:

The inter-group difference of objective response rate is compared by CMH Chi-square test.

Secondary efficacy endpoint analysis: Descriptive statistical analysis.

Progression-free survival is analyzed by Kaplan-Meier method;

Overall survival is analyzed by Kaplan-Meier method;

The inter-group difference of disease control rate is compared by CMH Chi-square test;

The duration of response is analyzed by Kaplan-Meier method; the median time to response and its 95% confidence interval are listed for the two groups.

Expansion part- primary efficacy endpoint analysis:

The 16-week progression-free survival rate is calculated in patients with advanced colorectal cancer who have failed with standard care and are receiving drug administration of 5 mg qd 3-week on/1-week off in the study. Secondary endpoints are analyzed by descriptive statistical analysis.

At the end of the trial, the survival (including median survival and 9-month survival rate) in patients with advanced colorectal cancer who have failed with standard care and are receiving drug administration of 5 mg qd 3-week on/1-week off is analyzed.

Safety analysis:

Safety analysis population: The safety analysis population includes the patients signing the informed consent who receive at least one dose of the treatment.

All safety parameters are summarized, and are tabulated by the safety population.

The frequency table (overall and by intensity) of adverse events is listed by system organ class. In the table of the overall incidence of adverse event, subjects with the same adverse event more than once is only counted once in the frequency table.

Shift table and frequency table are used simultaneously for summary of laboratory data according to sampling timepoint.

All the AEs and abnormal laboratory variables are evaluated according to CTCAE v4.0 grading system.

ECOG performance status will be summarized by descriptive statistics. Vital signs, ECG, and echocardiography will be described by tabulation.

During the randomized comparison part, inter-group differences are compared by CMH Chi-square test, based on the primary safety endpoints.

The overall incidence of adverse events, incidence of G3/4 adverse events, and severe adverse events are compared between the two groups;

The ratios of permanent discontinuation due to adverse events, and the ratio of interruption or reduced dose due to adverse events are compared between the two groups.

PK parameters:

WinNonlin enterprise version software is used for noncompartmental model analysis of plasma drug concentration.

Univariate analysis of variance is used for C_{max} , $AUC_{0-\infty}$ and AUC_{0-t} during the study using dose group as the fixed factor.

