Study start and end time	
The recruitment period for the randomized comparison part is estimated to be 8 months. The recruitment period for the expansion part is estimated to be 4 months.
 
Estimated start time: December 2012
 
Enrollment completion time for the expansion part: January 24, 2014
 
End time: October 24, 2014

Study objectives	
Primary objective:
 
To randomly compare the safety and tolerability of two different administration methods of Fruquintinib (4mg qd daily vs. 5mg qd 3-week on/1-week off) in treatment of patients with advanced colorectal cancer who have failed with standard care (evaluated according to CTCAE4.0), as to further determine the recommended dose for phase II/III clinical studies.
 
To further observe and evaluate the safety, tolerability and efficacy (progression-free survival) of Fruquintinib 5mg qd 3-week on/1-week off in treatment of patients with advanced colorectal cancer who have failed with standard care during the expansion

	part.
	
Secondary objective:
 
 To compare the objective response rate (ORR), disease control rate (DCR), duration of response (according to RECIST 1.1 criteria), progression-free survival (PFS) and overall survival (OS) between two groups To compare the pharmacokinetic profile of two different administration methods of Fruquintinib monotherapy in treatment of advanced colorectal cancer Expansion part- to further observe the DCR, ORR and OS of Fruquintinib in treatment of advanced colorectal cancer

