3.2 Number of subjects

The total sample size is 60 subjects.

Randomized comparison part: 20 subjects in each group, randomized (1: 1) into two dose groups.

Expansion part: 20 subjects.

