6.2 Clinical Assessment

6.2.1 Effectiveness

6.2.1.1 Effectiveness endpoint

All the effectiveness endpoints in the randomized comparison study are secondary endpoints.

Secondary endpoints:

Objective response rate (ORR) determined in accordance with RECIST1.1

Disease control rate (CR+PR+SD), where SD \geq 8 weeks

Duration of response

Progression-free survival (PFS)

Overall survival (OS)

Primary effectiveness endpoint in the expansion part is the progression-free survival at Week 16

The secondary endpoints are DCR, ORR and OS

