8.2.4 Interim Analyses

A interim analysis is performed when at least 30 subjects complete 4 cycles and 40 subjects complete 2 cycles of evaluation in the randomized comparison part of this study as to compare the safety and tolerability of two different administration methods of Fruquintinib. The primary parameters are statistically analyzed and combined with efficacy parameters

for comprehensive evaluation to determine the recommended dose group in phase II/III study for expansion part.

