8.3 Sample size

About 60 subjects are planned to be enrolled.

Here, 40 subjects are enrolled into the randomized comparison part, and approximately 20 more subjects are enrolled into the single-arm expansion part.

Randomized comparison part:

Group A (4 mg, qd, daily) consists of 20 patients;

Group B (5 mg, qd, 3-week on/1-week off) consists of 20 patients;

Expansion part:

Group B (5 mg, qd, 3-week on/1-week off) consists of approximately 20 patients.

9 Data Quality Assurance

Electronic data management system (DASforeCDM5.0) is used for this trial.

Establishment of electronic case report form (eCRF): eCRF is constructed by data administrator according to study protocol and medical record.

Allocation of authorities: the data administrators create the account respectively according to different identities, including investigator, sponsor, monitor and auditor, and are authorized different permissions to access eCDM. For example, investigators at each site can only find the content at their site and have the right to modify the data, the sponsor is limited only to look through all the cases; monitor and auditor can read the cases at each site, insert remarks or questions but have no right to modify the data.

Data entry: clinical investigators or their designated data entry clerk (clinical coordinator) enter the data from the medical records in the eCRF promptly and accurately. eCRF is not used as the original record, its content originates from medical records.

[figure not shown]
Questions on the data and answers: monitors monitor the data through eCDM and raise questions on line at any time when they find questions, the investigators answer the questions on line and modify wrong data, monitors could repeat their questions when necessary.

Data lock and export: the data are locked by the data administrator after each subject complete the trial and all the data are confirmed correct by the monitor, until the lock of the data from the last subject. The data are exported into the designated database by the data administrator after complete data lock, and submitted to statisticians for analysis.

eCRF is printed for archive at the end of study, if required. Data management center will maintain the electronic data until 5 years after its launch in the market. The data management center can open the system at any time after appointment during this period if

SFDA needs to check.

EDC System Emergency Plan

10 Study committee

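### PFS and OS are to be compared between the two regimens, but section 8.2.2 names a between-group test only for ORR and DCR

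*Protocol*

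**What the plan says.** The synopsis lists as a secondary objective the comparison of ORR, DCR, duration of response, "progression-free survival (PFS) and overall survival (OS) between two groups". Section 2.2 repeats this for the two administration methods.

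Section 8.2.2 then sets methods endpoint by endpoint for the randomized part:

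- ORR: inter-group difference by CMH chi-square test.
- A line reading "Secondary efficacy endpoint analysis: Descriptive statistical analysis", followed by the remaining endpoints.
- PFS: "Progression-free survival is analyzed by Kaplan-Meier method". OS has the same wording.
- DCR: "The inter-group difference of disease control rate is compared by CMH Chi-square test".
- Duration of response: Kaplan-Meier, with medians and 95% CIs for the two groups.

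The efficacy paragraph of the synopsis differs again: it plans only a statistical description of all five endpoints, which does not match the two CMH tests.

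On the use of the results, section 8.2.4 says of the interim: "The primary parameters are statistically analyzed and combined with efficacy parameters", in order to choose the regimen for the expansion part. Section 3.1.2 reports that interim (September 2013). It concludes that 5 mg 3-week on/1-week off was not inferior to 4 mg daily on efficacy, naming DCR and PFS in particular, and gives no hazard ratio, interval or margin.

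**The concern.** A Kaplan-Meier curve per arm describes each arm. It does not give a between-arm estimate or its uncertainty. The objective asks for a comparison of five endpoints, and the methods section supplies a test for two of them.

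The test also falls on the less informative member of a related pair. Section 6.2.1.1 counts stable disease towards DCR from 8 weeks, and section 6.2.1.2 puts the first scan after two 28-day cycles. DCR is therefore close to being progression-free at the first scan. Scans continue every 8 weeks until progression, but the tested endpoint uses almost none of that later information.

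At stake is whether the report can say how large a PFS difference between the regimens the data rule out. A claim of non-inferiority on PFS, even a preliminary one, needs that statement behind it.

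**Working it through.** **No planned figure to reproduce.** Section 3.2 says "Randomized comparison part: 20 subjects in each group, randomized (1: 1) into two dose groups". Section 8.3 gives head counts only, with no effect size, alpha, power or event count.

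**Inputs from the protocol.** 20 per arm; scans every 8 weeks; a 3.7-month median PFS from the interim summary in section 3.1.2. That summary says the median had reached 3.7 months with 3-week on/1-week off and had not reached 3.7 months with daily dosing. The wording does not settle which arm has the longer median, so both placements are used.

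**Assumptions.** Exponential PFS; hazard ratio (HR) 2.0 as base case; two-sided 5%; DCR taken as progression-free at Week 8; 4.345 weeks per month.

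**Week-8 disease control.** S(8 wk) = exp(−ln 2 × (8/4.345)/3.7) = exp(−0.345) = 0.708.

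- 3.7 months in the better arm: 0.708 against 0.708² = 0.502.
- 3.7 months in the worse arm: 0.708 against √0.708 = 0.842.

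**Log-rank power by formula.** Φ(√d/2 × |ln HR| − 1.96), with d PFS events. For d = 36: Φ(3 × 0.693 − 1.96) = Φ(0.119) = 55%. For d = 30 it is 48%, and for d = 40 it is 59%.

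**Simulation at HR 2.0.** Progression is dated to the 8-week scan; 4,000 trials per scenario, so Monte Carlo error is about one point.

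| Data | 3.7 months in | Log-rank, PFS | CMH, DCR |
|---|---|---|---|
| Final, no censoring | better arm | 54–55% | 26% |
| Final, no censoring | worse arm | 55% | 17% |
| Interim-type censoring | better arm | 41% | 25% |
| Interim-type censoring | worse arm | 29% | 18% |

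The interim rows assume 16–41 weeks of follow-up for 30 patients and 8–16 weeks for 10, built on the trigger in section 8.2.4.

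With 3.7 months in the better arm, other hazard ratios give, log-rank against DCR:

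- HR 1.5: 24% against 12% on final data; 17% against 11% at the interim.
- HR 2.5: 78% against 42% on final data; 64% against 43% at the interim.

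A final-data variant with 15% dropout and 3.7 months in the worse arm gives 48% against 15% at HR 2.0.

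**What 40 patients can show.** 80% power at HR 2.0 (equivalently 0.5) needs 4 × (1.96 + 0.842)²/(ln 2)² ≈ 66 events, more than the number randomized. With all 40 events, 80% power is reached only at |ln HR| = 2 × 2.802/√40 = 0.886, that is HR 0.41 or 2.4.

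**Width of the missing interval.** The 95% CI for the HR spans a factor exp(1.96 × 2/√d) either way: 2.00 for d = 32, 1.89 for d = 38. At an interim with 25–28 events it is 2.19 to 2.10.

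**What the interim DCR excludes.** The reported 76.4% and 83.3% fit 13/17 and 15/18. The difference is 6.9 points with standard error √(0.765 × 0.235/17 + 0.833 × 0.167/18) = 0.135, so the 95% CI is about −20 to +33 points. Power of a DCR test at those rates with 20 per arm is about 8%.

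**The case against.** **The SAP may supply the method.** The synopsis and section 8.2.3 defer detail to a statistical analysis plan that is not shown, and a log-rank test or Cox model is ordinary content for one. This stands as far as a missing log-rank line goes: its absence alone would be no finding. It does not remove the mismatch, because the protocol itself names which endpoints are compared between groups and uses a descriptive label that disagrees with its objective.

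**The split is loosely worded.** The DCR test sits under the same descriptive line as PFS and OS, so that line cannot mean that no between-group statistic is allowed. This stands. A reader might infer that a PFS comparison was deliberately ruled out; the text is too inconsistent for that.

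**PFS was looked at.** A reader might infer that the regimen choice rested on binary endpoints alone. Section 3.1.2 cites PFS as well as DCR, section 8.2.4 asks for an overall evaluation rather than a significance test, and Kaplan-Meier curves by arm would show divergence after Week 8. Only the formal testing is confined to ORR and DCR.

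**Efficacy is secondary here.** Section 6.2.1.1 says so, the primary safety endpoints do have between-group tests, and 20 per arm is too few for an efficacy conclusion on either scale. This limits the weight of the point and is why the interval matters more than the p-value.

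**Conclusion.** The point holds as a mismatch between objective and method. PFS and OS are to be compared, section 8.2.2 gives them no between-group statistic, and the synopsis describes the efficacy analysis in a third way.

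At HR 2.0, a PFS log-rank test has about 55% power on final data against 17–26% for DCR, and about 29–41% against 18–25% under assumed interim censoring. The direction was the same in every scenario tried. The size depends on the assumed hazard ratio, exponential shape, follow-up and arm placement, none of which the protocol states.

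Two stronger readings are not supported. One is that the efficacy comparison as a whole rests on a scale with half the power. The ratio runs from about a third to about two-thirds with the assumptions, PFS was also read descriptively, ORR is not a cut of PFS, and no cut of OS is tested. The other is that PFS should become the comparison that decides the regimen. This version already records 5 mg 3-week on/1-week off as selected after the September 2013 interim, so a final PFS test cannot inform that choice.

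What can still be improved is the final analysis, since section 8.2.3 has the analysis plan finalized before database lock.

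**What to change.** In section 8.2.2, for the randomized part, add text such as: PFS and OS are compared between groups A and B by the hazard ratio with 95% CI from a Cox model (Efron or exact handling of ties, because progression dates cluster at the 8-week scans) and by a log-rank test; both are exploratory, and Kaplan-Meier curves and medians with 95% CI are also given.

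Keep the CMH tests of ORR and DCR as supportive. Reword the descriptive line in 8.2.2 and the efficacy paragraph of the synopsis so that both agree with the objective. Where the report repeats the statement that one regimen was not inferior on PFS, put the hazard ratio and its interval beside it.

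The cost is a few sentences and a few lines of program, with no extra patients, visits or data. The downside is one or two more exploratory secondary comparisons with wide intervals, about a factor of 1.9–2.0 either way for PFS with 32–38 events.
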